#### A. Primary research question and objective.

Objective:	Objective 1: To examine incidence/prevalence of drug classes of interest.
	Objective 2: To assess duration of use and cumulative dose of products containing NOMAC or CMA.
	Objective 3: To describe users of relevant drug classes.
	Objective 4: To describe the line of treatment in users of products containing NOMAC or CMA.
	Objective 5: To describe the frequency of patients who develop meningioma during treatment with products containing NOMAC or CMA,

Authors: [name], [name], [name], [name], [name] Version: V4.0

Dissemination level: Public

	and the frequency of users who discontinue or switch to alternative treatments.
	Objective 6: To assess the impact of the restrictions of use in incident prescriptions of products containing NOMAC or CMA.
	All objectives will be focused on comparing changes before and after the implementation of restrictions.
Hypothesis:	Objective 1: N/A, descriptive analysis.
	Objective 2: Cumulative dose and duration of treatments with NOMAC or CMA will be lower after the implementation of restrictions.
	Objective 3: The number of new users of NOMAC or CMA will be reduced after the implementation of restrictions.
	Objective 4: The number of users initiating NOMAC or CMA as first-line treatment will be reduced after the implementation of restrictions.
	Objective 5: The number of switches and discontinuations from NOMAC or CMA to other drug classes will increase after the implementation of restrictions.
	Objective 6: The incidence of NOMAC or CMA will be reduced after the implementation of restrictions, especially for high-dose products. This reduction will not be observed for other drug classes of interest.
Population:	All objectives: The study population will be restricted to females aged >10 years old with >1 year of prior data history available.
	Additional criteria:
	Objective 1 (subgroup analysis): Individuals with a prior history of meningioma.
	Objective 2, 4 and 5: Individuals newly exposed to products containing NOMAC or CMA.
	Objective 3: Individuals newly exposed to drug classes of interest.
Exposure:	Objective 1: N/A
	Objective 2: First-ever prescription of NOMAC or CMA (assessed separately).
	Objective 3: First-ever prescription of drug classes of interest (any), including:
	- Combined hormonal contraceptives

Authors: [name], [name], [name], [name], [name] Version: V4.0

Dissemination level: Public

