	
 
Progestogens that are pregnadien derivates (including medroxyprogesterone and medroxyprogesterone alone)
 

	- Progestogen and oestrogen combination products.
	Objective 4: Same as Objective 2.
	Objective 5: Same as Objective 2.
	Objective 6: N/A
Comparator:	Before vs. After the implementation of restrictions
Outcome:	Objective 1: Prescribing of drug classes of interest (assessed separately)
	Objective 2: N/A (treatment duration and cumulative use of the exposure).
	Objective 3: N/A (characterisation of users)
	Objective 4: Prescribing of alternative treatments not containing NOMAC or CMA (assessed retrospectively to identify line of treatment).
	Objective 5: Number of patients diagnosed with meningioma during treatment and number of patients discontinuing treatment or switching to alternative treatments not containing NOMAC or CMA 180 days after the end of the index treatment.
	Objective 6: Prescribing of products containing NOMAC or CMA (assessed separately).
Time:	01/01/2010 to end of data availability
Setting:	Routinely collected data from 3 databases in 3 European countries.
Main measure of effect:	Objective 1:
	Incidence rates (new prescriptions per 100,000 person-years of the population at risk) and prevalence (proportions).
	Objective 2 to 5:
	- Objective 2: Median with minimum, maximum and interquartile range.
	- Objective 3-5: Counts and proportions
	
 
All objectives: Standardised Mean Differences (SMD) for comparing changes before and after the implementation of restrictions.
 

	Objective 6:
	Risk ratios derived from the interrupted time series analysis (ITS). ITS will be based on results obtained as part of Objective 1.

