## 8.7 Study size

The expected number of patients exposed to NOMAC or CMA is expected to be roughly between 1,900 in NAJS and 16,800 in IQVIA DA Germany and between 2,4004 in IQVIA LPD Belgium and 173,900 in IQVIA

<sup>2Specify whether a diagnosis code is required to be in the primary position (main reason for encounter)

<sup>3 These will include: meningioma, obesity, diabetes mellitus, type 2 neurofibromatosis, asthma, autoimmune diseases, epilepsy, uterine fibroids, menopause/perimenopause, primary ovarian insufficiency, endometriosis, polycystic ovarian syndrome, menstrual disorders, neoplasm of the endometrium, neoplasm of the brain, neoplasm of the breast, cancer (any malignancy), hyperlipidaemia, hypertensive disorder, osteoporosis, venous thromboembolism.

<sup>4 These will include: progestogen and oestrogen combination products not containing NOMAC or CMA, progestogens that are pregnadien derivates not containing NOMAC or CMA, progestogen and oestrogen combination products not containing NOMAC or CMA, NOMAC, CMA, medroxyprogesterone, antidepressants, metformin, bisphosphonates, clonidine, gonadotropin releasing hormone antagonists and anti-androgens.

Authors: [name], [name], [name], [name], [name]

Version: V4.0

**Dissemination level:** Public

DA Germany, respectively. These counts were provided as part of the feasibility assessment and correspond to the entire source data, without restriction on age, sex or study period.

No specific sample size calculations have been performed. Given that meningioma is a rare tumour, we expect to have limited sample size in Objective 1, when restricting the population to individuals with prior history of meningioma. For Objective 3, 4 and 5, we expect an adequately large sample size to estimate Standardised Mean Differences (SMD) accurately. For Objective 2, this might be more limited as we will only consider users initiating treatment within a period of 6 to 12 months.

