Several factors have been identified to potentially influence the power to estimate the impact of the intervention, including the total number of time points, the average sample size per time point, the expected effect size, the location of intervention in time series or the impact model used.(20) In previous studies, ITS have been found to have more than 80% power to detect effect sizes of 1.0 or greater in a range of situations with 24 or more points, depending on the degree of autocorrelation and the impact model used.(21) Unbalanced designs (i.e. unequal number of time points before and after the intervention) have been found to have less power than balanced designs.(20, 21) As the intervention is located at the end of the time series, we will delay the study period start to balance the number of observations for Objective 6 and to ensure a more recent contrafactual for comparison (see "8.8 Analysis").

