#### Objective 6:

The impact of the restrictions of use will be estimated using an ITS. This analysis will be restricted to NOMAC and CMA (assessed separately) and will be informed by results of the main analysis obtained as part of objective 1 (no meningioma restriction). For NOMAC, the intervention taken place in 2018 will also be assessed.

Time series will be assessed using segmented regression. Monthly incident counts of patients prescribed with NOMAC or CMA will be modelled using a Poisson regression model. Quasi-Poisson models will be considered in the presence of overdispersion. The effect size of the intervention will be estimated using risk ratios (RR).

The assumption of linearity will be assessed by visually inspecting the data and residuals, as well as through statistical goodness-of-fit tests. Autocorrelation will be assessed by examining the plot of residuals and the partial autocorrelation function and conducting statistical tests where possible. If seasonality is detected, it will be controlled for by including variables representing them in the regression model. If the trends are not (or cannot be transformed to be linear) or in the presence of residual autocorrelation, ITS will not be conducted due to the complexity of predicting the counterfactual and to disentangle the intervention effects.(23)

Authors: [name], [name], [name], [name], [name]

Version: V4.0

Dissemination level: Public

The impact model of the intervention (i.e. how we expect the intervention has impacted the outcome) is anticipated to show an abrupt change in the level and a gradual change in the gradient of the trend (step and slope change). Potential impact models will be further discussed and agreed with EMA and defined a priori.(23, 24)

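### Objective 6 does not say which risk ratio from its anticipated step-and-slope model answers the hypothesis of reduced incidence

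*Protocol*

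**What the plan says.** - Protocol section 7, Table 1, main measure of effect for Objective 6: "Risk ratios derived from the interrupted time series analysis (ITS". The word is plural, and no coefficient, contrast or month is attached to it.
- Table 1, hypothesis for Objective 6, repeated in Table 11: "The incidence of NOMAC or CMA will be reduced after the implementation of restrictions, especially for high-dose products". This is one directional statement.
- Section 8.8, Objective 6, on the model: "Monthly incident counts of patients prescribed with NOMAC or CMA will be modelled using a Poisson regression model", with quasi-Poisson in reserve for overdispersion.
- Same section, on the effect measure: "The effect size of the intervention will be estimated using risk ratios (RR".
- Same section, on the expected shape: the impact is "anticipated to show an abrupt change in the level and a gradual change in the gradient of the trend (step and slope change". The next sentence adds: "Potential impact models will be further discussed and agreed with EMA and defined a priori".
- Section 8.7: "No specific sample size calculations have been performed".
- The 2022 analysis uses data from January 2021 (section 8.8). November 2022 to January 2023 are left out (section 8.6.3), and the last six months are left out of Objectives 1 and 6 in the paragraph on the two IQVIA databases (section 11).

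**The concern.** A step-and-slope model has two intervention parameters, so its risk ratio k months into the post-intervention period is exp(level + k x slope change). There are then as many ratios as post-intervention months, plus a ratio for the change in trend. The hypothesis is about whether incidence fell, and nothing links it to any of them.

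The likely default is the level ratio, exp(level). That describes one instant at the start of a very short series, where the fitted line is least well determined. Because three months are dropped, it also depends on where time since intervention is set to zero, and the protocol does not state this. Objective 6 is the only regression-based estimate of the impact of the measures. The choice of ratio could end up being made after the results are seen.

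**Working it through.** **The plan's own figure.** For series of at least 24 time points, section 8.7 relies on outside work: "ITS have been found to have more than 80% power to detect effect sizes of 1.0 or greater in a range of situations". The protocol does not give that work's model, autocorrelation or definition of effect size, so the figure cannot be reproduced or called wrong. It clearly depends on the parameter tested. With 24 balanced points, a shift of one standard deviation, least squares and no autocorrelation, power is 65% for a mean shift without trend and 21% for the level coefficient of a step-and-slope model.

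**Inputs from the protocol.**
- Pre-intervention: January 2021 to October 2022, 22 months. Three months are dropped.
- Germany: lock 30-09-2023, less six months, gives February to March 2023 = 2 post-intervention months.
- Belgium: lock 31-12-2023, less six months, gives February to June 2023 = 5.
- Croatia: lock 17-11-2023, complete months only, gives February to October 2023 = 9 (3 if the six-month exclusion also applied there).

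**Assumptions (not in the protocol).** Two-sided 5% level, constant true ratio 0.8, flat underlying trend, Poisson variation, no autocorrelation or seasonality, and 50, 200 or 1,000 new users a month.

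**Method.** Log-linear Poisson model with intercept, month, post indicator and post x months since February 2023. The covariance matrix is the inverse of X'WX, with W the expected counts. With n post-intervention months, the average effect is level + m x slope change, where m = (n - 1)/2, and

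Var(average) = Var(level) + m² Var(slope) + 2m Cov(level, slope).

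Results at 50 a month (log scale):

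| Post months | SE level | SE slope | Correlation | SE average | Reduction |
|---|---|---|---|---|---|
| 2 | 0.175 | 0.224 | -0.63 | 0.136 | 22% |
| 5 | 0.144 | 0.050 | -0.65 | 0.110 | 24% |
| 9 | 0.123 | 0.021 | -0.52 | 0.107 | 13% |

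Example, 5 months: 0.144² + 4 x 0.050² - 4 x 0.65 x 0.144 x 0.050 = 0.0207 + 0.0100 - 0.0187 = 0.0120, and its square root is 0.110. All standard errors scale with 1/√(count), so the percentage reductions hold at any count. For a true ratio of 0.7 the reductions are 23%, 25% and 15%.

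**Power.** Φ(d - 1.96) + Φ(-d - 1.96), with d = |ln 0.8|/SE = 0.223/SE.
- 50 a month: level 25/34/44%, average 37/53/55% (2/5/9 months). A step-only model gives 37/53/57%.
- 200 a month (SEs halved): level 72/87/95%, average 91/98/99%.
- 1,000 a month: all about 100% with February coding.

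**Where time zero is put.** If time is counted from November 2022, the level is extrapolated back three months:

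Var(level, November) = Var(level) + 9 Var(slope) - 6 Cov(level, slope).

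For 5 months: 0.0207 + 0.0225 + 6 x 0.65 x 0.144 x 0.050 = 0.0713, so SE = 0.267 instead of 0.144. For 2 and 9 months it is 0.79 and 0.165. The average over the included months is the same number under either coding.

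The estimate moves too. Suppose the true ratio falls log-linearly from 0.95 to 0.70 over five months. The slope change is ln(0.70/0.95)/4 = -0.0763 a month. The level ratio is 0.95 with February coding and 0.95 x exp(3 x 0.0763) = 1.19 with November coding. The average is √(0.95 x 0.70) = 0.82 under both.

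**The case against.** **The model is only anticipated, and the contrast is ordinary analysis-plan detail.** This carries weight: the text is under-defined and does not contradict itself. But what is deferred for agreement with EMA is the shape of the effect. Agreeing on step and slope, as expected, is what creates several ratios. Table 1 already sets out a main measure and a hypothesis, and these do not meet.

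**Section 8.6.3 starts the post-intervention period in February 2023.** That favours February coding, but it defines the comparison period and not the origin of the time variable.

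**One average can hide a growing or rebounding effect.** This is correct, and it is the reason to keep the level and slope ratios in the report.

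Stronger readings that a reader might infer, and that the protocol does not support:
- *That the protocol promises a single ratio.* It writes the plural. A level and a trend ratio together are compatible with the wording.
- *That the two coefficients often disagree.* With a constant ratio of 0.8 their signs differ in 50 to 58% of series (50 to 200 a month), but this is what a true slope change of zero implies. Both are significant and opposite in only about 2 to 3%, and in 0.5% or less if the effect grows from 0.9 to 0.7. It is common (12 to 63%) only under a rebound, where level down and slope up is an accurate description.
- *That the false-positive rate doubles.* Claiming a reduction on either coefficient gives about 5.0% against a nominal 2.5% under no effect. The protocol states no such rule and no significance level, and its overall aim is descriptive.
- *That fitting step and slope loses power in general.* The average contrast has practically the power of a step-only model. The loss arises only if the level alone, or both coefficients, must carry the claim.

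**Conclusion.** The point holds as an undefined main measure: no section says which ratio from the anticipated model answers the Objective 6 hypothesis. Choosing the post-period average instead of the February-coded level lowers the standard error by about 13 to 25% on the log scale, whatever the monthly count, and removes the dependence on the time origin. What this means for power is conditional. The difference is appreciable at 50 or 200 new users a month, absent at 1,000 with February coding, and of little use at 10 a month, where either measure has low power. The figures rest on the Table 3 locks, on assumed counts and ratios, and on a simple Poisson series. A later data cut would lengthen the post-intervention series. The matter is most pressing for Germany, where two post-intervention months are fitted exactly by step and slope.

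**What to change.** In Table 1 and section 8.8, if step and slope is the agreed impact model:

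- Name as the main Objective 6 measure the geometric-mean ratio of fitted to counterfactual incidence over a stated post-intervention window, exp(level + slope change x mean post time), with its 95% confidence interval from the same fitted model.
- Code post time from the first included post-intervention month.
- Report the level and slope ratios alongside, so that a growing or fading effect stays visible.
- State how many months are averaged in each database.
- Give the 2018 NOMAC analysis an end date before the 2020 restrictions and the pandemic period. Section 8.8 now says only from January 2017 onwards, and section 11 gives the pandemic as the reason for not assessing the 2020 restrictions.

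The cost is a few sentences and one linear contrast from a model already planned, with no new data. The small downside is that the averaging window differs between databases, so the ratios are not strictly comparable across them. No meta-analysis is planned, so this matters only for interpretation.

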## 8. RESEARCH METHODS

## 8.1 Study type and study design

Retrospective cohort studies will be conducted using routinely collected health data from 3 databases from 3 countries in Europe. The study will comprise of:

- 4. A population-level drug utilisation study (DUS) to assess incidence/prevalence of drug classes of interest (objective 1).
- 5. A patient-level DUS to describe:
  - a. Treatment duration and cumulative dose (objective 2).
  - b. Characteristics of new users (objective 3)
  - c. Line of treatment (objective 4)
  - d. Switching to alternative treatments (objective 5)
- 6. A trend analyses and RMM effectiveness to assess changes in:
  - a. Patient-level analyses (objective 2 to 5)
  - b. Population-level analyses (objective 6, based on results of objective 1)

The study types with related study designs are described in Table 2.

**Table 2.** Description of potential study types and related study designs.

Study type	Study design	Study classification
Population Level DUS	Population Level Cohort	Off the shelf
Patient-level DUS	Cohort analysis	Off the shelf
Trend analyses and RMM	Population-level cohort and New	Complex
effectiveness	drug user cohort	

## 8.2 Study setting and data sources

This study will be conducted using routinely collected data from 3 databases in 3 European countries selected from the DARWIN EU® Database Catalogue. All databases were previously mapped to the Observational Medical Outcomes Partnership (OMOP) Common Data Model (CDM).

The selection process was based on the size of the databases, the number of individuals exposed to drug classes of interest, the suitability of denominator population for population-level rates, geographical spread, and available follow-up data. Based on the feasibility assessment performed, the suggested databases are considered fit for purpose:

- 1. IQVIA Disease Analyzer Germany (IQVIA DA Germany)
- 2. IQVIA Longitudinal Patient Database Belgium (IQVIA LPD Belgium)
- 3. Croatian National Public Health Information System (NAJS), Croatia

Information on data sources planned to be used with a justification for their choice in terms of ability to capture the relevant data is described in **Table 3**.

Authors: [name], [name], [name], [name], [name] Version: V4.0

Dissemination level: Public

**Table 3.** Description of the selected data sources.

Country	Name of Database 	Justification for Inclusion	Health Care setting 	Type of Data 	Number of active subjects 	Feasibility count of NOMAC 	Feasibility count of CMA 	Data lock for the last update
Germany	IQVIA DA Germany	Suitable denominator population for population-level rates.  Observed records of individuals exposed to nomegestrol and chlormadinone.  Contribute to the geographical diversity of data sources.	Primary care	EHRS	4.35M	16.8k	173.9k	30-09-2023
Belgium	IQVIA LPD Belgium	Suitable denominator population for population-level rates.  Follow-up data up to > 1 year after the implementation of restrictions of use.  Observed records of individuals exposed to nomegestrol and chlormadinone.  Contribute to the geographical diversity of data sources.	Primary care	EHRS	213k	6.7k	2.4k	31-12-2023

DARWIN EU® Coordination Centre

Authors: [name], [name], [name], [name], [name]

Version: V4.0

**Dissemination level: Public** 

Country	Name of Database 	Justification for Inclusion	Health Care setting 	Type of Data 	Number of active subjects 	Feasibility count of NOMAC 	Feasibility count of CMA 	Data lock for the last update
Croatia	NAJS	Suitable denominator population for population for population-level rates.  Follow-up data up to 1 year after the implementation of restrictions of use.  Observed records of individuals exposed to nomegestrol and chlormadinone.  Contribute to the geographical diversity of data sources.	Primary care, hospital care (IP, OP)	Registry	2.68M	1.9k	15.3k	17-11-2023

- 1. IQVIA DA= IQVIA Disease Analyzer; IQVIA LPD= IQVIA Longitudinal Patient Database; NAJS= Croatian National Public Health Information System
- 2. IP= inpatient, OP= outpatient.
- 3. EHR = Electronic health records
- 4. Defined as the maximum number of persons in an observation period in the last 6 month
- 5. Person counts provided as part of the feasibility assessment using preliminary concepts. Counts correspond to the whole database, without restriction on age, sex or study period. All counts are rounded to the nearest multiple of 100. NOMAC= Nomegestrol acetat; CMA = Chlormadinone acetate.

Authors: [name], [name], [name], [name], [name]

Version: V4.0

Dissemination level: Public

#### IQVIA Disease Analyzer (IQVIA DA) Germany, Germany

IQVIA Disease Analyzer (DA) Germany is a database of de-identified electronic medical records from specialised and GP practices in Germany since 1992. This dataset encompasses approximately 3% of all outpatient practices within Germany, ensuring a substantial representation of the national healthcare landscape. The sampling methods used for practice selection, considering physician's demographics, specialty focus, community size category and federal state location, was instrumental in constructing a database that accurately mirrors the diverse spectrum of healthcare providers in the country. Consequently, data within IQVIA DA Germany database has been demonstrated to be representative of general and specialised practices throughout Germany.

The database contains demographics records, basic medical data, disease diagnosis, and prescription records. While the database partly records information on deaths and procedures, it currently does not support linkage with external data sources. Routine updates are conducted at regular intervals. The quality of data is assessed based on several criteria including completeness of information and correctness (e.g. linkage between diagnosis and prescriptions).

